2.4.3 CLINICAL STUDIES OF IPILIMUMAB IN CANCER

Ipilimumab has been studied in various solid tumors both as a single agent and in combination with nivolumab. Ipilimumab as a single agent is currently approved in melanoma. Ipilimumab in combination with Nivolumab is currently approved in melanoma, renal cell carcinoma, and MSI-H/dMMR Metastatic Colorectal Cancer.

Ipilimumab is currently being used in trials with HNSCC patients. This includes NCT02823574 Ipilimumab Versus Nivolumab in Combination With Ipilimumab Placebo in Patients With Recurrent or Metastatic Squamous Cell Carcinoma of the Head and Neck (CheckMate 714) and NCT02741570 An Open Label, Randomized, Two Arm Phase III Study of Nivolumab in Combination With Ipilimumab Versus Extreme Study Regimen (Cetuximab + Cisplatin/Carboplatin + Fluorouracil) as First Line Therapy in Recurrent or Metastatic Squamous Cell Carcinoma of the Head and Neck (HNSCC). Preliminary efficacy or toxicity data is not currently available from these trials.

Ipilimumab is associated with inflammatory events resulting from increased or excessive immune activity, likely to be related to its mechanism of action. These Immune-related adverse events (irAEs) are defined as AEs that are 1) related to ipilimumab per investigator and 2) consistent with an inflammatory process. The most common treatment-related AEs associated with the use of ipilimumab were immune related (named immune-related AEs or irAEs), reflecting ipilimumab's mechanism of action. The irAEs primarily involved the GI tract (e.g., diarrhea and colitis); skin (e.g., pruritus and rash); and, less frequently, the liver (e.g., transaminase elevations), endocrine glands (including the thyroid, pituitary and adrenal glands, manifested by hypothyroidism, hypophysitis with hypopituitarism, or adrenal insufficiency, respectively), and nervous system (e.g., motor neuropathy with or without sensory neuropathy). Immune-related AEs were generally manageable using symptomatic or immuno-suppressive therapy as recommended through detailed diagnosis and management guidelines. In the sections below efficacy and toxicity of single agent ipilimumab as well as combination Ipilimumab and Nivolumab is discussed.

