8.4.3 Preparation and administration

Relatlimab injections (10 mg/mL) can be co-administered with nivolumab injection (also referred to as BMS-936558 injection) as an IV infusion through a compatible low-protein-binding in-line filter at the protocol-specified doses. Total infusion volume not to exceed 160 mL for flat dose. For patients weighing less than 40 kilograms (kg), the total volume of infusion must not exceed 4 mL per kg of patient weight. Relatlimab injections (10 mg/mL) may be mixed with nivolumab injection (10 mg/mL) as follows:

- Relatlimab injections (10 mg/mL) may be mixed with nivolumab injection (10 mg/mL) at a ratio of 1:3 and the resultant drug product solution may be diluted with either NS or D5W to a total protein concentration no lower than 0.8 mg/mL (0.2 mg/mL of relatlimab and 0.6 mg/mL of nivolumab). No incompatibilities have been observed between the combined drug product solutions and EVA, PO, or PVC IV containers, DEHP-plasticized PVC IV sets, DEHP-free IV sets and in-line filters with 0.2 µm or 1.2 µm PES, 0.2 µm nylon, or 0.2 µm PVDF membranes.

Care must be taken to assure sterility of the prepared solution, as the products do not contain any anti-microbial preservative or bacteriostatic agent.

Nivolumab and relatlimab are to be co-administered as a 60 minute IV infusion, using a volumetric pump with a 0.2 micron to 1.2 micron pore size, low protein binding (polyethersulfone membrane) in-line filter at the protocol-specified dose. It is not to be administered as an IV push or bolus injection. . At the end of the infusion, flush the line with a sufficient quantity of normal saline (approximately 15-20 mL).

8.5 Potential Side Effects of the Study Drug Treatments (please refer to the current investigator brochures for a complete list of all potential side effects)

NIVOLUMAB COMBINED WITH IPILIMUMAB

Very common side effects (may affect more than 10% of people)

- ALT increased: lab test result associated with abnormal liver function
- AST increased: lab test result associated with abnormal liver function
- Diarrhea
- Fatigue
- Itching
- Fever
- Nausea
- Rash

Common side effects (may affect 5 to 10% of people)

- Abdominal pain
- Adrenal gland function decreased
- Alkaline phosphatase increased: lab test result associated with liver or bone abnormalities

- Amylase increased: lab test result associated with pancreas inflammation
- Appetite decreased
- Bilirubin (liver function test) increased
- Chills
- Constipation

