12.3 ADVERSE EVENT TREATMENT DISCONTINUATION CRITERIA

1. Any Grade ≥ 2 drug-related uveitis, eye pain or blurred vision that does not respond to topical therapy and does not improve to Grade 1 severity within the re-treatment period OR requires systemic treatment
2. Any Grade ≥ 3 non-skin, drug-related AE lasting > 7 days, or recurs with the following exceptions for laboratory abnormalities, diarrhea, colitis, neurologic toxicity, drug-related uveitis, pneumonitis, bronchospasm, hypersensitivity reactions, infusion reactions, and endocrinopathies:
 - a. Grade ≥ 3 drug-related myocarditis, diarrhea, colitis, neurologic toxicity, uveitis, pneumonitis, bronchospasm, hypersensitivity reaction, or infusion reaction of any duration requires discontinuation:-- Grade ≥ 3 drug-related endocrinopathies, adequately controlled with only physiologic hormone replacement do not require discontinuation. Adrenal insufficiency requires discontinuation regardless of control with hormone replacement.
 - b. Grade > 3 drug-related laboratory abnormalities do not require treatment discontinuation except:
 - i. Grade > 3 drug-related thrombocytopenia > 7 days or associated with bleeding requires discontinuation
 - c. Any drug-related liver function test (LFT) abnormality that meets the following criteria require discontinuation:
 - i. Grade > 3 drug-related AST, ALT or Total Bilirubin requires discontinuation*
 - ii. Concurrent AST or ALT $> 3 \times$ ULN and total bilirubin $> 2 \times$ ULN
- * In most cases of Grade 3 AST or ALT elevation, study treatment will be permanently discontinued. If the investigator determines a possible favorable benefit/risk ratio that warrants continuation of study treatment, a discussion between the investigator and the Sponsor
3. Any Grade 4 drug-related adverse event or laboratory abnormality (including but not limited to creatinine, AST, ALT, or Total Bilirubin), except for the following events which do not require discontinuation:
 - Grade 4 neutropenia ≤ 7 days
 - Grade 4 lymphopenia or leukopenia or asymptomatic amylase or lipase
 - Isolated Grade 4 electrolyte imbalances/abnormalities that are not associated with clinical sequelae and are corrected with supplementation/appropriate management within 72 hours of their onset

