 - Grade 4 drug-related endocrinopathy adverse events, such as, hyper- or hypothyroidism, or glucose intolerance, which resolve or are adequately controlled with physiologic hormone replacement (corticosteroids, thyroid hormones) or glucose-controlling agents, respectively, may not require discontinuation after discussion with and approval from the Sponsor.
4. Any event that leads to delay in dosing lasting > 6 weeks from the previous dose requires discontinuation, with the following exceptions:
 - Dosing delays to allow for prolonged steroid tapers to manage drug-related adverse events are allowed. A drug related adverse event where steroids are not indicated but the management of the adverse event causes a dose delay lasting > 6 weeks may be allowed if approved by the Sponsor.
 - Dosing delays lasting > 6 weeks from the previous dose that occur for non-drug-related reasons may be allowed if approved by the Sponsor.
5. Any adverse event, laboratory abnormality, or intercurrent illness which, in the judgment of the Investigator, presents a substantial clinical risk to the participant with continued study drug combination dosing.
6. Prior to re-initiating treatment in a participant with a dosing delay lasting > 6 weeks, the sponsor must be consulted. Tumor assessments should continue as per protocol even if dosing is delayed. Periodic study

visits to assess safety and laboratory studies should also continue if clinically indicated during such dosing delays.

7. Subjects who meet criteria for permanent discontinuation should receive no further study therapy. The following exceptions apply:

- If the toxicity resolves to < Grade 1 or baseline > 6 weeks after last dose, but the subject does not otherwise meet the criteria for permanent discontinuation and the Investigator believes that the subject is deriving clinical benefit, then the subject may be eligible to resume the study drug(s) following the approval of the sponsor.
- Subjects with a grade 4 drug-related amylase and/or lipase increase that is not associated with symptoms or clinical manifestations of pancreatitis can be restarted on therapy once the levels have recovered to grade 3 or less, and after consultation with the sponsor.
- Subjects with baseline Grade 1 AST, ALT, or total bilirubin who require dose delays for reasons other than a drug-related hepatic event may resume treatment in the presence of Grade 2 AST, ALT, or total bilirubin.

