- Subjects who require dose delays for drug-related elevations in AST, ALT, or total bilirubin may resume treatment when these values have returned to their baseline CTCAE Grade or normal, provided the criteria for permanent discontinuation are not met.
- Subjects may resume treatment in the presence of Grade 2 fatigue.
- Drug-related endocrinopathies adequately controlled with only physiologic hormone replacement may resume treatment.

12.4 INFUSION REACTIONS:

Treatment recommendations are provided below and may be modified based on local treatment standards and guidelines, as appropriate:

For Grade 1 symptoms (Mild reaction; infusion interruption not indicated; intervention not indicated):

- Remain at bedside and monitor subject until recovery from symptoms. The following prophylactic premedications are recommended for future infusions: diphenhydramine 50 mg (or equivalent) and/or acetaminophen/paracetamol 325 to 1000 mg at least 30 minutes before additional study drug administrations.

For Grade 2 symptoms (Moderate reaction requires therapy or infusion interruption but responds promptly to symptomatic treatment [e.g., antihistamines, non-steroidal anti- inflammatory drugs, narcotics, corticosteroids, bronchodilators, IV fluids]; prophylactic medications indicated for ≤ 24 hours).

- Stop the infusion, begin an IV infusion of normal saline, and treat the subject with diphenhydramine 50 mg IV (or equivalent) and/or acetaminophen/paracetamol 325 to 1000 mg; remain at bedside and monitor subject until resolution of symptoms. Corticosteroid and/or bronchodilator therapy may also be administered as appropriate. If the infusion is interrupted, then restart the infusion at 50% of the original infusion rate when symptoms resolve; if no further complications ensue after 30 minutes, the rate may be increased to 100% of the original infusion rate. Monitor subject closely. If symptoms recur, then no further study drug will be administered at that visit.
- For future infusions, the following prophylactic premedications are recommended:
- Diphenhydramine 50 mg (or equivalent) and/or acetaminophen/paracetamol 325 to 1000 mg should be administered at least 30 minutes before study drug infusions.
- If necessary, corticosteroids (up to 25 mg of SoluCortef or equivalent) may be used.

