12.5 CRITERIA TO RESUME TREATMENT

Subjects may resume treatment with combination therapy when the drug-related AE(s) resolve(s) to Grade \leq 1 or baseline and if applicable the patient is no longer on systemic steroids, with the following exceptions:

- Subjects may resume treatment in the presence of Grade 2 fatigue.
- Subjects who have not experienced a Grade 3 drug-related skin AE may resume treatment in the presence of Grade 2 skin toxicity.
- For participants with Grade 2 AST, ALT and/or Total Bilirubin Abnormalities, dosing may resume when laboratory values return to baseline and management with corticosteroids, if needed, is complete.
- Drug-related pulmonary toxicity, diarrhea, or colitis must have resolved to baseline before treatment is resumed. Subjects with persistent Grade 1 pneumonitis after completion of a steroid taper over at least 1 month may be eligible for retreatment if discussed with and approved by the Sponsor.

Participants with drug-related endocrinopathies adequately controlled with only physiologic hormone replacement may resume treatment after consultation with the Sponsor.

Adrenal insufficiency requires discontinuation regardless of control with hormone replacement.

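### Section 12.3 item 7 lets hormone-controlled endocrinopathies resume without excluding adrenal insufficiency, which item 2a and Section 12.5 say must stop

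*Combined protocol and SAP*

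**What the plan says.** Section 12.3 sets the criteria for stopping study treatment because of adverse events. Item 2a exempts Grade 3 or higher endocrinopathies that are controlled by hormone replacement, then takes one condition back out: "Adrenal insufficiency requires discontinuation regardless of control with hormone replacement". Section 12.5, on resuming treatment, repeats that sentence without a grade limit. Just before it, Section 12.5 says: "Participants with drug-related endocrinopathies adequately controlled with only physiologic hormone replacement may resume treatment after consultation with the Sponsor".

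Item 7 of Section 12.3 opens with "Subjects who meet criteria for permanent discontinuation should receive no further study therapy. The following exceptions apply" and lists six bullets. The last reads: "Drug-related endocrinopathies adequately controlled with only physiologic hormone replacement may resume treatment".

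Item 3 has a separate exception for Grade 4 endocrinopathies that have settled or are held in check by treatment. Its closing words are: "physiologic hormone replacement (corticosteroids, thyroid hormones) or glucose-controlling agents, respectively, may not require discontinuation after discussion with and approval from the Sponsor".

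**The concern.** Adrenal insufficiency is an endocrinopathy that hormone replacement can control, so the item 7 bullet covers it by its plain terms. Item 7 presents its bullets as exceptions to permanent discontinuation, which is what item 2a imposes. An investigator working from the exception list could therefore conclude that a patient with replaced adrenal function may go back on study therapy, when two other places in Section 12 say that patient must stop. For the other controlled endocrinopathies, item 7 omits the Sponsor step that Section 12.5 attaches in a nearly identical sentence. At stake is the consistency of a dosing instruction that protects patients.

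**Working it through.** No arithmetic decides this point; it is a comparison of texts.

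**1. Is adrenal insufficiency within item 7's bullet?** Section 2.4.3 describes immune-related events in "endocrine glands (including the thyroid, pituitary and adrenal glands, manifested by hypothyroidism, hypophysitis with hypopituitarism, or adrenal insufficiency, respectively". The protocol thus treats it as an endocrine immune-related event, and the bullet has no carve-out.

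**2. The rules side by side, for a drug-related event controlled by hormone replacement**

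| Place | Adrenal insufficiency | Other endocrinopathies | Sponsor's part |
|---|---|---|---|
| 12.3 item 2a (under a Grade 3 or higher item) | Stop | Need not stop | None stated |
| 12.3 item 3 (Grade 4) | Not excluded | Might not need to stop | Discussion and approval |
| 12.3 item 7, last bullet | Not excluded, so may resume | May resume | None stated |
| 12.5 (no grade stated) | Stop | May resume | Consultation |

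Item 7 conflicts with item 2a and Section 12.5 in the second column and differs from Section 12.5 in the last. Because Section 12.5 states the adrenal rule without a grade, the conflict does not depend on grade.

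**3. Does another limit in item 7 remove the conflict?** The first bullet requires that the patient not otherwise meet the criteria for permanent discontinuation, and also requires Sponsor approval. The amylase and lipase bullet requires Sponsor consultation. The bullet on dose delays for drug-related liver-test elevations applies "provided the criteria for permanent discontinuation are not met". The endocrine bullet's only condition is adequate control with physiologic replacement alone. That is exactly the condition that item 2a and Section 12.5 say makes no difference for adrenal insufficiency.

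**4. Is there a rule of precedence?** No text in Section 12 says which statement governs when item 7 and item 2a or Section 12.5 disagree. The endocrinopathy algorithm in Appendix II is a figure that is not reproduced in the text available here, so nothing is inferred from it either way.

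**5. Could the situation arise?** Section 8.5 lists decreased adrenal gland function for nivolumab plus ipilimumab under "Common side effects (may affect 5 to 10% of people". The list gives no grade, dose or attribution, and Section 2.4.7 says ipilimumab toxicity depends on dose. The entry supports plausibility and no more.

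**The case against.** The strongest reply is that the protocol already answers the question. The adrenal rule is specific, mandatory and stated twice, each time directly after the general permission it limits; item 7 is general and permissive. Section 12.5 is the section on resumption, Section 12.2 holds both drugs until retreatment criteria are met, and nothing in item 7 waives Section 12.5. Several item 7 bullets, such as the one on Grade 2 fatigue, are ordinary resumption criteria, so the lead-in cannot be taken literally for all of them. Most of this stands, and it is why stopping is the better reading. It does not remove the defect: the lead-in still labels the endocrine bullet an exception to permanent discontinuation, and a reader has to work out the hierarchy unaided.

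Four stronger readings are tempting, and the documents do not support them.

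- *The patient would be re-dosed with both study drugs.* Item 7 does not say so. Under Section 7.5 the fourth and last ipilimumab dose is at C5D14 and nivolumab alone follows from C6D1, so this would be wrong for any later resumption in that regimen.
- *There would be no Sponsor check.* That holds only if item 7 is read alone. Section 12.5 requires consultation, and item 6 of Section 12.3 requires it before restarting after a delay of more than 6 weeks. The trial is also run by a Sponsor-Investigator at one institution, which limits the practical weight of the omission.
- *The conflict is likely to affect patients.* If 20 of the 40 patients received ipilimumab, rates of 5 to 10% would give 20 × 0.05 = 1 to 20 × 0.10 = 2 events, and a chance of at least one of 1 − 0.95^20 = 64% to 1 − 0.90^20 = 88%. At an assumed 1% the chance is 1 − 0.99^20 = 18%. These are chances of a listed event of any kind. They are not chances of a drug-related, controlled case in which staff follow item 7 against the other two statements.
- *The toxicity pausing rule is affected.* Section 15.3.2 counts events sufficient to warrant discontinuation under Section 12.3. Item 7's lead-in presupposes that such a criterion has been met, so the wording of the bullet does not by itself show that any count would change.

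**Conclusion.** The inconsistency is real. Read literally, item 7's last bullet permits study therapy to resume in a patient with controlled adrenal insufficiency, whom item 2a and Section 12.5 require to stop. It also leaves out the Sponsor consultation that Section 12.5 requires for other controlled endocrinopathies. Stopping is the better reading and very probably the intended one, but the protocol does not say that it prevails. How many patients this would touch cannot be quantified from the documents. The conclusion rests on the wording alone and needs no assumption about event rates. This is a minor drafting correction to a safety rule, worth making because it is cheap; it does not bear on the design, endpoints or analysis.

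The item 3 wording is a lesser gap. It names corticosteroids among the replacements and does not exclude adrenal insufficiency, but it covers Grade 4 events only and already needs Sponsor approval.

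**What to change.** In the last bullet of Section 12.3 item 7, insert *(except adrenal insufficiency)* after the word for endocrinopathies, and end the sentence with the same Sponsor-consultation condition as Section 12.5. Alternatively, delete the bullet's text and refer the reader to Section 12.5, so that the rule stands in one place.

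Optionally, for consistency, insert *(except adrenal insufficiency)* in item 3's Grade 4 endocrinopathy bullet.

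Neither edit sets new policy; both apply the rule the protocol already states twice. The cost is one or two short wording changes in an amendment, with no change to sample size, monitoring tables or data collection.

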12.5 CRITERIA TO RESUME TREATMENT

Subjects may resume treatment with combination therapy when the drug-related AE(s) resolve(s) to Grade \leq 1 or baseline and if applicable the patient is no longer on systemic steroids, with the following exceptions:

- Subjects may resume treatment in the presence of Grade 2 fatigue.
- Subjects who have not experienced a Grade 3 drug-related skin AE may resume treatment in the presence of Grade 2 skin toxicity.
- For participants with Grade 2 AST, ALT and/or Total Bilirubin Abnormalities, dosing may resume when laboratory values return to baseline and management with corticosteroids, if needed, is complete.
- Drug-related pulmonary toxicity, diarrhea, or colitis must have resolved to baseline before treatment is resumed. Subjects with persistent Grade 1 pneumonitis after completion of a steroid taper over at least 1 month may be eligible for retreatment if discussed with and approved by the Sponsor.

Participants with drug-related endocrinopathies adequately controlled with only physiologic hormone replacement may resume treatment after consultation with the Sponsor.

Adrenal insufficiency requires discontinuation regardless of control with hormone replacement.

13.0 ASSESSMENT OF DISEASE

13.1 DEFINITIONS

Measurable Lesions: Lesions that can be accurately measured in at least one dimension with longest diameter at least >10 mm on CT scan (or >20 mm by X-ray). Cystic lesions thought to represent cystic metastasis can be considered as measurable lesions.

Malignant Lymph Nodes: To be considered pathologically enlarged and measurable, a lymph node must be > 15 mm when assessed by CT scan.

Non-measurable Lesions: All other lesions < 10 mm or lymph nodes < 15 mm by CT scan.

Target Lesions: All measurable lesions up to a maximum of 2 lesions per organ and up to 5 lesions in total, representative of all involved organs, should be identified as target lesions and recorded and measured at baseline. Target lesions should be selected on the basis of their size (lesions with the longest diameter), be representative of all involved organs, but in addition should be those that lend themselves to reproducible repeated measurements. It may be the case that, on occasion, the largest lesion does not lend itself to reproducible measurement. In this circumstance, the next largest lesion which can be measured reproducibly should be selected. A sum of the diameters (longest for non-nodal lesions, short axis for nodal lesions) for all

target lesions will be calculated and reported as the baseline sum diameters. If lymph nodes are to be included in the sum, then only the short axis is added into the sum. The baseline sum diameters will be used as reference to further characterize any objective tumor regression in the measurable dimension of the disease.

Non-target Lesions: All other lesions (or sites of disease) including any measurable lesions over and above the 5 target lesions should be identified as non-target lesions and should also be recorded at baseline.

Measurements of these lesions are not required, but the presence, absence, or in rare cases unequivocal progression of each should be noted throughout follow-up.

